6.10. Interim Analysis

No interim analysis will be conducted.

After all subjects have completed the Week 16 Visit (or discontinued from the study), a Week 16 data restriction will be performed, the primary data analysis will be conducted **CC1** **CC1** **CC1**. However, unblinded data will only be made available to select Sponsor and Contract Research Organization (CRO) team members involved with analysis of the data **CC1**. All other Sponsor, site, and CRO personnel directly involved with the conduct of the study, will remain blinded to treatment assignments until the final database lock at the conclusion of the study. At the end of the study, after all subjects have completed, or have been discontinued from the Apremilast Extension Phase (Weeks 16 to 32) and the Observational Follow-up Phase, the final analysis will be performed and a final Clinical Study Report will be generated.

7. SUMMARY OF SUBJECT DISPOSITION

The number of subjects screened, the number and percentage of subjects randomized (as recorded in the IVRS database) and not randomized among all subjects screened will be summarized. The failed inclusion/exclusion criteria of subjects who were screened and not randomized will be included in the summary. The above percentages will be based on the number of subjects screened.

The number and percentage of subjects included in the ITT population, safety population, and PP population will be summarized by treatment arm; the percentages will be based on the number of subjects randomized.

For the Double-blind Placebo-controlled Phase, the number and percentage of subjects who entered, completed, and discontinued, as well as the number and percentage of primary reasons for discontinuation will be summarized.

All subjects who terminated early or completed the study treatment will be asked to continue into the Post-treatment Observational Follow-up Phase. The primary reasons for discontinuation are collected in the screening disposition, treatment disposition and follow-up disposition eCRF and will be summarized with the following categories:

- Screen failure (screening only)
- Death
- Adverse event(s)
- Pregnancy
- Lack of efficacy (treatment disposition only)
- Withdrawal by subject
- Non-compliance with study drug (treatment disposition only)
- Lost to follow-up
- Study terminated by sponsor
- Protocol deviation
- Physician decision
- Other
- Site terminated by sponsor (treatment disposition only)

The number and percentage of subjects randomized will be tabulated by treatment and study site. The percentages will be based on the number of subjects randomized.

Subject disposition will be provided by treatment arm and protocol phase:

- Placebo-controlled Phase – Weeks 0 to 16: in addition to the tabulation of subjects who are randomized, or included in the ITT, PP, and Safety populations, the number and percent of subjects who completed and entered the next phase (Weeks 16 to 32), completed but did not enter the next phase, and discontinued early will be provided. The

primary reasons for early discontinuation will also be tabulated. Subjects who complete and entered the next phase include subjects who have IP dispensed at Week 16/Visit 7, subjects who completed but did not enter the next phase include subjects who have either a Week 16 visit or a termination visit no earlier than the Week 16 visit window, and discontinued early subjects include those who discontinued prior to the Week 16 visit window.

- Apremilast Extension Phase – Weeks 16 to 32: The number and percent of subjects who entered the phase, took at least one dose of IP, completed the phase, discontinued early, and primary reason for discontinuation will be provided.
- Observational Follow-up Phase (4 weeks): Summary will include all subjects who entered Follow-up phase and whether completed Follow-up following the above phases.

The number and percentage of subjects randomized by study site and treatment group will be tabulated. The percentages will be calculated based on the number of subjects who are randomized.

CELGENE PROPRIETARY INFORMATION

8. DEMOGRAPHICS AND BASELINE CHARACTERISTICS

Summaries for the demographics, baseline characteristics, prior medication/procedure, and concomitant medications/procedure will be presented for the ITT population by treatment group and overall. Individual subject listings will also be provided.

8.1. Demographics

Summary statistics will be provided for the following continuous variables:

- Age (years)
- Weight (kg)
- Height (cm)
- Baseline Body Mass Index (BMI; kg/m²)

Number and percentage will be provided for the following categorical variables:

- Age category (< 65, ≥ 65)
- Age category (< 40, ≥ 40 to < 65, ≥ 65 to < 75, ≥ 75 to < 85, ≥ 85 years)
- Sex (Male, Female)
- Race (American Indian or Alaska Native, Asian, Black or African American, Native Hawaiian or Other Pacific Islanders, White, Other)
- Ethnicity (Hispanic or Latino, Not Hispanic or Latino)
- Geographical region (USA, Canada)
- Alcohol History (Yes, No)
- Tobacco use (Never Smoked, Past Smoker, Current Smoker)
- Baseline BMI category (< 18.5, ≥ 18.5 to < 25, ≥ 25 to < 30, ≥ 30 to < 35, ≥ 35 to < 40, ≥ 40 kg/m²)

BMI will be calculated as follows: BMI (kg/m²) = Weight (kg)/ Height (m²). Other variables (i.e., age, weight, height, sex, race, ethnicity, geographical region, alcohol history and tobacco use history) will be summarized as recorded from the eCRF.

8.2. Baseline or Disease Characteristics

Baseline clinical characteristics will be summarized descriptively by treatment group, which will include the following:

- Duration of plaque psoriasis (from date of diagnosis to the date of informed consent; year, presented one digit after the decimal point)
- Duration of plaque psoriasis categories (< 10, ≥ 10 to < 20, ≥ 20 years)
- Baseline ScPGA score

- Baseline whole body itch NRS score
- Baseline scalp itch NRS score
- Baseline DLQI total score
- Baseline DLQI total score category (0 to 3, 4 to 10, 11 to 20, 21 to 30)

- Number of prior phototherapies (0, 1, 2, ≥ 3)
- Number of failed prior phototherapies for subjects who had prior phototherapies (0, 1, 2, ≥ 3)
- Number of prior conventional systemic therapies (0, 1, 2, ≥ 3)
- Number of failed prior conventional systemic therapies for subjects who had prior conventional systemic therapies (0, 1, 2, ≥ 3)
- Number of prior biologic therapies (0, 1, 2, ≥ 3)
- Number of failed prior biologic therapies for subjects who had prior biologic therapies (0, 1, 2, ≥ 3)
- Number of prior systemic therapies (0, 1, 2, ≥ 3)
- Number of failed prior systemic therapies for subjects who had prior systemic therapies (0, 1, 2, ≥ 3)
- Number of prior topical scalp psoriasis medications or shampoo treatments (0, 1, 2, ≥ 3)
- Number of failed prior scalp psoriasis medications or shampoo treatments for subjects who had prior scalp psoriasis medications or shampoo treatments (0, 1, 2, ≥ 3)

8.3. Medical History

A summary of relevant medical history and concomitant diseases will be presented by system organ class (SOC) and preferred term (PT) according to the Medical Dictionary for Regulatory Affairs (MedDRA) version 20.0 or higher, using frequency distributions (counts and percentages). A similar summary will be generated for the currently active diagnosis only.

8.4. Prior and Concomitant Procedures

Prior procedures are defined as those started before the start of the study treatment (whether or not ended before the start of the study treatment).

For a study phase, concomitant procedures are defined as those started during the phase. Study phases are defined in Section 5.1.1. Prior procedures and concomitant procedures will be coded using the MedDRA dictionary Version 20.0 or higher.

A frequency tabulation of the number of subjects with each prior procedure will be given for the ITT population by treatment group, system organ class (SOC), and preferred term (PT).

A frequency summary of concomitant procedures will be provided for the safety population by treatment group, SOC, and PT.

8.5. Prior and Concomitant Medications

Prior medications are defined as medications that were started before the start of the study treatment and either ended before the start of the study treatment or continued after study treatment.

For a study phase, concomitant medications are defined as non-study medications started during the phase, or started before the phase and ended or remain ongoing during the phase. Study phases are defined in Section 5.1.1. The Anatomical Therapeutic Chemical (ATC) coding scheme of the World Health Organization Drug Dictionary (WHO DD version DDE B2 March 2017 or higher) will be used to group medications into relevant categories. A frequency summary of prior medications will be provided by treatment group, ATC2 level, and standardized medication name for the safety population.

Prior psoriasis medications will be summarized with baseline characteristics.

Concomitant medications documented during the study will be summarized. The frequency tabulation will display the number (%) of subjects receiving at least one concomitant medication, the number (%) of subjects receiving at least one medication within a relevant category, and each concomitant medication by treatment group. The summaries will be provided for (1) Placebo-controlled Phase (Weeks 0 to 16), (2) Apremilast Extension Phase (Weeks 16 to 32), and (3) Observational Follow-up Phase (4 weeks).

9. STUDY TREATMENTS AND EXTENT OF EXPOSURE

9.1. Treatment Duration

Treatment duration will be summarized by treatment group for the analysis phases (Section 5.1.1) and for the Apremilast-exposure Period (Section 5.1.2). Subjects who are treated in the corresponding phases or period will be used, i.e., the safety population for Placebo-controlled Phase (Weeks 0 to 16), and the apremilast subjects as treated population for the Apremilast-exposure Period, etc.

Summary statistics for treatment duration (in weeks), as well as a frequency summary of treatment duration categories (e.g., < 4, \geq 4 - < 8 weeks, etc.), will be provided.

9.1.1. Placebo-controlled Phase – Weeks 0 to 16

Treatment duration (in weeks) is calculated from the date of the first dose of IP at Week 0/Visit 2 to either the date one day prior to the first dose date in the Apremilast Extension phase for the IP dispense at Week 16/Visit 7, or the date of the last dose of IP in the study for subjects who discontinue in the phase. Imputation rule for partially or completely missing last dose date is specified in [Appendix A1A1.1.4](#)

Treatment duration will be summarized by actual treatment (placebo vs. apremilast 30 mg BID) for the safety population.

9.1.2. Apremilast Extension Phase – Weeks 16 to 32

Treatment duration is calculated from the first dose date in the Apremilast Extension phase for the IP dispense at Week 16/Visit 7 to the date of the last dose of IP in the study for subjects who discontinue in the phase or who complete the study at Week 32/Visit 10. Imputation rule for partially or completely missing last dose date is specified in [Appendix A1A1.1.4](#)

9.1.3. Apremilast-exposure Period

Treatment duration for Apremilast-exposure Period (Section 5.1.2) is calculated from the date of the first dose of apremilast 30 mg BID, which is the date of the first dose of apremilast after randomization at Week 0/Visit 2 or switched to apremilast at Week 16/Visit 7, to the last apremilast dose date for subjects who discontinue in the first 32 weeks or who complete the study at Week 32/Visit 10. Imputation rule for partially or completely missing last dose date is specified in [Appendix A1A1.1.4](#)

9.2. Treatment Compliance

As part of the routine recording of the amount of IP taken by each subject, the numbers of tablets dispensed and/or returned will be recorded at each visit (except Week 3/ Visit 1). These records will be used to calculate treatment compliance.

The treatment compliance (in %) for each subject will be computed as 100 times the total number of tablets taken (the total number of tablets dispensed minus the total number of tablets

returned) over the analysis phase or period divided by the intended total number of tablets that should have been taken over the same phase or period.

Summary statistics for compliance (%) will be provided by treatment for each analysis phase or period. Frequency summary tables of compliance will also be presented with the following categories: < 75%, >= 75% - <= 120%, and > 120%. A subject data listing of drug accountability records will be provided.

9.2.1. Placebo-controlled Phase – Weeks 0 to16

Treatment compliance will be calculated for the treatment duration in the phase specified in Section 9.1.1 and will be summarized by treatment group for ITT population.

9.2.2. Apremilast Extension Phase – Weeks 16 to 32

Treatment compliance will be calculated for the treatment duration in the phase specified in Section 9.1.2 and will be summarized by treatment group for the subset of ITT population who entered the phase.

9.2.3. Apremilast-exposure Period

Treatment compliance will be calculated for the treatment duration in the period specified in Section 9.1.3.

Treatment compliance will be summarized for apremilast 30 mg BID treatment for apremilast as treated population.

10. PROTOCOL DEVIATIONS AND IMPORTANT PROTOCOL DEVIATIONS

Protocol deviations and important protocol deviations will be categorized by Clinical Research Physician (CRP). A list of protocol deviations and important protocol deviations for all subjects for week 16 analysis will be defined prior to the Week 16 data restriction and unblinding (i.e., prior to the unblinding of double-blind placebo-controlled phase data). The list of protocol deviations and important protocol deviations for all subjects for final analysis will be finalized prior to the final database lock. This listing of important protocol deviations for week 16 analysis will also identify which subjects are to be removed from the per-protocol population.

Protocol deviations and important protocol deviations will be summarized by treatment. Summary tables showing the number and percent of subjects with at least one protocol deviation/important protocol deviation and by each protocol deviation/important protocol deviation will be provided. Listings of subjects with protocol deviations and important protocol deviations will also be provided.

CELGENE PROPRIETARY INFORMATION

11. SAFETY ANALYSIS

Safety will be assessed via descriptive statistics and point estimates. Unless otherwise specified, all safety analyses described in this section will be performed for both the Placebo-controlled Phase and the Apremilast-exposure Period. The safety analyses for the Placebo-controlled Phase will be based on the safety population and presented by treatment group (placebo, and apremilast 30 mg BID), and the safety analyses for the Apremilast-exposure Period will be based on the apremilast subjects as treated population and presented by apremilast dose group (i.e., apremilast 30 mg BID) irrespective of the start time of apremilast exposure (at Week 0 or 16).

For the analyses of AEs and marked abnormalities, the following point estimates are distinguished:

- Subject incidence: Subject incidence (i.e., percentage [%] used in a frequency summary) is defined as the number of subjects with the specific event divided by the number of subjects included in the analysis. Subjects with multiple occurrences of the specific event in the specific analysis period will be counted only once in the numerator.
- Exposure-adjusted incidence rate (EAIR) per 100 subject-years: The EAIR per 100 subject-years is defined as 100 times the number of subjects with the specific event divided by the total exposure time (in years) among subjects included in the analysis. Subjects with multiple occurrences of the specific event in the specific analysis period will be counted only once in the numerator. The exposure time for a subject without the specific event is the treatment duration, whereas the exposure time for a subject with the specific event is the treatment duration up to the start date (inclusive) of the first occurrence of the specific event. The total exposure time in years is calculated by dividing the sum of exposure time in days over all subjects included in the analysis by 365.25. The EAIR per 100 subject-years is interpreted as the expected number of subjects with at least one occurrence of the specific event per 100 subject-years of exposure to the IP.

AEs and marked abnormalities will be summarized by subject incidence and EAIR for the Placebo-controlled Phase (Weeks 0 to 16) and for the Apremilast-exposure Period. In addition, selected summaries for the Apremilast Extension Phase (Weeks 16 to 32) and the Observational Follow-up Phase (4 weeks) will be presented.

Descriptive statistics will be provided for vital signs, weight, laboratory values (continuous measurements) by treatment and visit, including the end of treatment visits. The baseline value, value at the time point, and change from baseline will be summarized for subjects who have values at baseline and at the time point.

Shift tables, that is, tables that summarize the baseline categories (normal, abnormal) versus the category at the end of the respective periods or versus the worst post-baseline category, include subjects who have values at baseline and at least one post-baseline value. Similarly, in frequency summaries of shifts from baseline at scheduled study weeks per protocol, only subjects who have values at baseline and at the time point will be included.

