### **9.7. Safety Analysis**

The safety analyses will be performed using the safety population as defined in Section 9.2. Safety will be assessed by clinical review of all relevant parameters including treatment-emergent adverse events (TEAEs), laboratory tests, vital signs, and ECG measurements; no inferential testing for statistical significance will be performed.

Adverse events will be classified using the Medical Dictionary for Regulatory Activities (MedDRA) classification system. Adverse events will be tabulated for the Placebo-controlled Phase (Weeks 0 to 16) and the Apremilast Exposure Phase in the study. All TEAEs will be summarized by system organ class, preferred term, severity, and relationship to IP. Adverse

events leading to death or to IP withdrawal and serious AEs will also be summarized and listed separately.

Data from other safety assessments will be summarized descriptively. Shift tables for laboratory parameters showing the number of subjects with values low, normal, and high compared with the normal reference ranges pre-treatment versus post-treatment will be provided.

To account for the different exposure to the investigational product, adverse events or marked laboratory abnormalities will also be summarized using the exposure adjusted incidence rate, in addition to the simple incidence rates.

By-subject listings will be provided for all relevant safety data.

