11.3. Clinical Laboratory Evaluations

The endpoints for clinical laboratory evaluations include:

- Laboratory marked abnormalities (see [Appendix A2](#))
- Observed value and change from baseline over time in the following laboratory parameters
 - Hematology: hemoglobin, hematocrit, platelet, erythrocytes, leukocytes, basophils/leukocytes, eosinophils/leukocytes, lymphocytes/leukocytes, monocytes/leukocytes, neutrophils/leukocytes, basophils, eosinophils, lymphocytes, monocytes, and neutrophils
 - Serum chemistry: glucose, lactate dehydrogenase (LDH), bicarbonate, calcium, chloride, potassium, magnesium, phosphate, sodium, blood urea nitrogen, creatinine, urate, total cholesterol, high-density lipoprotein cholesterol (HDL-C), low-density lipoprotein cholesterol (LDL-C), triglycerides, alkaline phosphatase, AST (SGOT), ALT (SGPT), total bilirubin, albumin, and total protein
- Shifts from baseline to post-baseline time points and to the worst post-baseline value in terms of normal/abnormal (low or high) in the above hematology and serum chemistry parameters

Summary statistics of observed values and changes from baseline in laboratory parameters will be provided over time. Frequency summaries (shift tables) of shifts from baseline to post-baseline time points and to the worst post-baseline value in terms of normal/abnormal will be provided.

Laboratory marked abnormalities will be summarized; subject incidence and EAIR for each abnormality will be calculated based on subjects with a baseline value and at least one post-baseline value for criteria requiring baseline or subjects with at least one post-baseline value for criteria not requiring baseline. A subject data listing of laboratory marked abnormalities will be provided. Laboratory marked abnormalities will also be summarized for subjects with normal values at baseline and for subjects with abnormal values at baseline separately. For the purposes of these summaries, subjects with abnormal (normal) values at baseline are defined as those whose baseline value is low (not low) for criteria concerning low values and those whose baseline value is high (not high) for criteria concerning high values; both low and high are relative to the laboratory normal range.

A subject data listing of all laboratory data, including urinalysis, will be provided.

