11.4. Vital Signs and Weight

The endpoints for vital signs and weight include:

- Observed value and change from baseline over time in vital signs (temperature, pulse, and blood pressure)
- Shifts from baseline to post-baseline time points and to the worst post-baseline value in terms of normal/abnormal in pulse and blood pressure (normal ranges are defined as: 60-100 beats/minute for pulse, 90-140 mmHg for systolic blood pressure, and 60-90 mmHg for diastolic blood pressure)

- Observed value, change and percent change from baseline over time in weight

Summary statistics of observed values and changes from baseline in vital signs (including weight, for which percent change from baseline will also be summarized) will be provided over time. Frequency summaries (shift tables) of shifts from baseline to post-baseline time points and to the worst post-baseline value in terms of normal/abnormal will be provided for pulse and blood pressure.

Frequency summaries of change and percent change in weight from baseline to the end of the period will be provided by baseline BMI category (< 25 , ≥ 25 to < 30 , ≥ 30 to < 35 , ≥ 35 to < 40 , and ≥ 40 kg/m²) and by baseline weight category (< 70 , ≥ 70 to < 85 , ≥ 85 to < 100 , and ≥ 100 kg). The categories of weight change (kg) and percent change (%) are < -20 , ≥ -20 to < -10 , ≥ -10 to < -5 , ≥ -5 to < 0 , 0 , > 0 to ≤ 5 , > 5 to ≤ 10 , > 10 to ≤ 20 , and > 20 . The end-of-period or end-of-phase value is the last post-baseline value in the analysis period or phase (excluding the value obtained at the follow-up visit, if applicable) up to 28 days after the last dose of IP in the study.

A subject data listing of all vital signs and weight data will be provided.

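### SAP shift tables for pulse and blood pressure merge low with high values, and the laboratory shift wording is inconsistent within the SAP and, in its general definition, departs from the protocol's low/normal/high

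*SAP*

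**What the plan says.** Protocol 9.7 commits to laboratory shift tables "showing the number of subjects with values low, normal, and high compared with the normal reference ranges", before against after treatment. It makes no such commitment for vital signs; other safety assessments are to be summarized descriptively, without inferential testing.

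The SAP addresses shift tables in three places:

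- **SAP 11 (general definition):** "tables that summarize the baseline categories (normal, abnormal) versus the category at the end of the respective periods or versus the worst post-baseline category".
- **SAP 11.3 (laboratory):** the endpoint bullet describes shifts "in terms of normal/abnormal (low or high) in the above hematology and serum chemistry parameters". The later sentence stating what will be produced omits the qualifier: "Frequency summaries (shift tables) of shifts from baseline to post-baseline time points and to the worst post-baseline value in terms of normal/abnormal will be provided".
- **SAP 11.4 (vital signs):** shifts are "in terms of normal/abnormal in pulse and blood pressure". The normal ranges given there are 60-100 beats/minute for pulse, 90-140 mmHg for systolic and 60-90 mmHg for diastolic pressure. The output sentence also uses two categories.

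SAP 11, 11.3 and 11.4 all tabulate a worst post-baseline value or category. None says which direction is worse when a parameter can be abnormal on either side.

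**The concern.** A range with a lower and an upper limit has two ways of being abnormal, and they usually mean different things clinically. A table that records only normal or abnormal counts a subject who drops below range together with one who rises above it. It also shows a subject who goes from above range to below range as abnormal at both times, which is no shift. Two arms with opposite patterns can then produce the same table.

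Safety and tolerability against placebo is the first-listed secondary objective, and the shift table is where a reader looks for the number of subjects who crossed a limit. For laboratory data there is a further difficulty: the protocol states three categories, and a programmer working from the SAP's general definition and the 11.3 output sentence would build two.

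**Working it through.** The documents give no figure for shift tables, so there is none to reproduce. The check has four parts.

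**1. Texts side by side**

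| Data | Protocol 9.7 | SAP general definition (11) | SAP specific section: endpoint | SAP specific section: output sentence |
|---|---|---|---|---|
| Laboratory | low, normal, high | normal, abnormal | normal/abnormal, qualified as low or high (11.3) | normal/abnormal (11.3) |
| Pulse, blood pressure | no categories promised | normal, abnormal | normal/abnormal (11.4) | normal/abnormal (11.4) |

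The vital-sign row is uniform: two categories throughout. In the laboratory row, two of the three SAP statements give two categories. The third can mean that abnormal is split into low and high, or only that abnormal covers both.

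**2. What a strictly two-category table hides**

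Share abnormal = share low + share high. This is an illustration with assumed rates. Take 300 subjects at 2:1, so 300 × 2/3 = 200 on apremilast and 300 × 1/3 = 100 on placebo, all normal at baseline. A share x moves low on apremilast and the same share moves high on placebo.

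| x (assumed) | Apremilast low / normal / high | Placebo low / normal / high | Two-category abnormal, apremilast vs placebo |
|---|---|---|---|
| 5% | 10 / 190 / 0 | 0 / 95 / 5 | 5% vs 5% |
| 10% | 20 / 180 / 0 | 0 / 90 / 10 | 10% vs 10% |
| 20% | 40 / 160 / 0 | 0 / 80 / 20 | 20% vs 20% |

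The pattern need not be all-or-nothing. With normal-to-high at 10% vs 4% and normal-to-low at 4% vs 10%, both arms show 10% + 4% = 4% + 10% = 14%. Two 6-point differences disappear.

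**3. What the other planned outputs supply**

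SAP 11.3 lists 15 hematology and 22 chemistry parameters, 15 + 22 = 37. Compared with the marked-abnormality criteria in SAP Appendix A2:

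- Limits on both sides: 7 (calcium, glucose, phosphate, potassium, sodium, hemoglobin, platelets).
- A limit on one side only: 15 (for example magnesium, high only; leukocytes, lymphocytes and neutrophils, low only).
- No limit: 15 (for example hematocrit, erythrocytes, eosinophils, bicarbonate, chloride, HDL-C, LDL-C, total protein).

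So 15 + 15 = 30 of 37 lack a marked-abnormality count in at least one direction. Pulse and blood pressure have no criteria in Appendix A2, so they lack one in both directions. Some marked limits also lie well outside the reference range (ALT and AST at three times the upper limit), so those tables do not count crossings of the reference limit itself.

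**4. The worst value**

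In a two-category table, worst can only mean that the subject was abnormal at least once, with no direction. In a three-category table, a subject with one low and one high value has no defined worst category. Either way a rule is missing.

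**The case against.** The strongest reply concerns the laboratory tables. SAP 11.3 is the section that specifies them, and its endpoint bullet carries the low-or-high qualifier. A specific section normally governs a general one, the output sentence may be shorthand for the endpoint just listed, and the sentence in SAP 11 is partly there to set the denominator. On that reading the SAP agrees with the protocol. This stands as a possible reading. It is why a reader should not infer that the SAP has definitely dropped the protocol's commitment. It does not remove the inconsistency.

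A reader might also infer that the protocol's low/normal/high promise covers all safety shift tables. It covers laboratory parameters only. The vital-sign tables go beyond what Protocol 9.7 asks for and contradict nothing in it.

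A reader might further infer that the planned safety output as a whole cannot show direction. The documents do not support that. Signed changes from baseline are summarized by treatment and visit for laboratory values and vital signs, with minimum and maximum. All the data are listed by subject. Seven analytes have separate low and high criteria. Under Protocol 10.3 a laboratory abnormality that needs treatment or is judged clinically important becomes an adverse event and is tabulated as such. These points stand. What remains uncovered is the number of subjects crossing each reference limit when the value was not reported as an adverse event.

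The rates in the illustration are chosen to cancel, and nothing in the documents predicts mirror-image effects. A high-to-low move on the SAP ranges also needs a large change: more than 140 − 90 = 50 mmHg systolic, 90 − 60 = 30 mmHg diastolic, or 100 − 60 = 40 beats/minute. Such moves may be few, and the more ordinary loss is the merging of normal-to-low with normal-to-high.

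**Conclusion.** The point holds in three parts, with different certainty.

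- **Pulse and blood pressure:** as written, the shift tables lose direction. This is a weakness in the analysis, not a conflict with the protocol.
- **Laboratory parameters:** the SAP is inconsistent with itself and, on its general definition, departs from Protocol 9.7. Whether direction would actually be lost depends on how the 11.3 qualifier is read, and the text does not settle it.
- **Worst post-baseline value:** it has no defined direction for a two-sided range in any of the three sections.

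The loss is limited to frequency counts of subjects crossing each limit. It matters most for the 30 of 37 laboratory parameters without a two-sided marked-abnormality criterion, and for pulse and blood pressure, which have none. How many subjects would be affected cannot be estimated from the documents. The tables are descriptive, so alpha, power and the efficacy analyses are untouched. The conclusion assumes that the tables are programmed as the SAP words them.

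**What to change.** In SAP 11, 11.3 and 11.4, define shift tables as baseline low, normal or high against post-baseline low, normal or high. Use the laboratory reference range for laboratory parameters and the ranges already given in 11.4 for pulse and blood pressure. Make the endpoint bullet and the output sentence in 11.3 say the same thing. For two-sided ranges, replace the single worst column with one for the lowest and one for the highest post-baseline value.

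No new data are needed. The values are collected, the vital-sign ranges are stated, and SAP 11.3 already classifies baseline laboratory values as low or high when it splits the marked-abnormality tables. The cost is a wording change and slightly larger tables: 3 × 3 = 9 cells instead of 2 × 2 = 4 per comparison, and two extreme-value columns instead of one. It is best made before the Week 16 data are unblinded, when the SAP is due to be final.
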